### 3.2 Hypothesis

The combined administration of two infusions of 3BNC117 (30 mg/kg) together with six infusions of romidepsin (5 mg/m^2) will prevent or delay the return of HIV-1 viremia during an analytical treatment interruption compared with administration of romidepsin alone.

### 3.3 Aims

#### Primary Objective:

- Evaluate the effects of romidepsin plus 3BNC117 or romidepsin alone on delaying or preventing viral rebound in ART-treated HIV-1-infected individuals during an analytical interruption of ART.

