
	
 
a. Absolute neutrophil count <math>\leq</math> 1,000 cells/<math>\mu</math>l
 
b. Hemoglobin < 11 gm/dL
 
c. Platelet count < 125,000 cells/<math>\mu</math>l
 

Inclusion / Exclusion Criteria
	
 
d. ALT <math>\geq</math> 1.25 x ULN
 
e. AST <math>\geq</math> 1.25 x ULN
 
f. Total bilirubin > 1.0 ULN
 
g. eGFR < 60 mL/min/1.73m^2
 
17. Any vaccination within 14 days prior to 3BNC117 administration
 
18. Receipt of any therapeutic HIV vaccine in the past
 
19. Receipt of any anti-HIV monoclonal antibody in the past, or HDAC inhibitor of any kind in the past 2 years.
 
20. Participation in another clinical study of an investigational product currently or within past 12 weeks, or expected participation during this study.
 

Study Product, Dose, Route, Regimen
	
- 3BNC117 (RUhumab-001) is a recombinant, fully human monoclonal antibody (mAb) of the IgG1<math>\kappa</math> isotype that specifically binds to the CD4 binding site (CD4bs) within HIV-1 envelope gp-120.
 
- Romidepsin is an HDAC inhibitor that has emerged as one of the potent inducers of HIV-1 transcription. Romidepsin displays isoform specificity towards class I HDACs, which are particularly important to maintaining HIV-1 latency. Romidepsin will be provided by Celgene for use in this study.
 
In Group A, one intravenous infusion of 3BNC117 mAb (30 mg/kg) will be administered at week 0 and a second infusion at week 8 via a peripheral vein over 60 minutes.
 
In Groups A and B, one intravenous infusion of romidepsin (5 mg/m^2) will be administered at weeks 0, 1, and 2 (treatment cycle 1), and weeks 8, 9, and 10 (treatment cycle 2), via a peripheral vein over 120 minutes (Figure 1). In Group A, the start of each romidepsin cycle will begin 2 days after the 3BNC117 infusion.

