#### Secondary Objectives:

- Evaluate the safety of romidepsin plus 3BNC117 or romidepsin alone in ART-treated HIV-1 infected individuals;
- Evaluate the effects of romidepsin plus 3BNC117 or romidepsin alone on the size of the HIV-1 reservoir in ART-treated HIV-1-infected individuals;

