### 4 Study Design

The design is a randomized interventional phase 2a trial of romidepsin with or without 3BNC117 in HIV-1-infected patients on ART, conducted as a multi-center study at the Department of Infectious Diseases, Aarhus University Hospital, Denmark, the Rockefeller University Hospital, USA, and the University Hospital of Cologne, Germany. Enrollment will be competitive; it is anticipated that each site will enroll approximately 10 participants.

[figure not shown]
Participants will be randomized 1:1 in a non-blinded fashion to receive one of two regimens:

- A) Two treatment cycles each consisting of 3BNC117 infusions (30mg/kg) + three romidepsin infusions (5mg/m^2); or
- B) Two treatment cycles each consisting of three romidepsin infusions (5mg/m^2).

ART will be discontinued 16 weeks after the start of the second treatment cycle (analytical treatment interruption, ATI) and subjects will be monitored closely for viral rebound. The study outline is shown in **Figure 1**. The targeted enrolment is 30 subjects (15 per arm).

Leukapheresis will be performed before and after the two treatment cycles to guarantee sufficient material to investigate changes in the reservoir after the interventions.

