### 2. Size of the functional HIV-1 reservoir:

The size of the functional HIV-1 reservoir will be determined by the number of infectious unit per  $10^6$  resting memory CD4+ T cells (IUPM) using a viral outgrowth assay before (week -2) and after therapy, just before ATI (week 22). Paired student t-test or paired Wilcoxon test will be used to determine changes in reservoir size from baseline to the pre-ATI time-point for each group.

Total HIV-1 DNA, episomal HIV-1 DNA (2-LTR), and unspliced HIV-1 RNA in circulating total CD4+ T cells will also be determined at baseline (week -2, week 0), before and after each treatment cycle, at the pre-ATI time point (week 24), and at the end of the study (week 48). A 95% repeated measures ANOVA F-test will be used to compare changes in these variables during the study.

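### The primary and reservoir objectives are worded as effects of each regimen, but with romidepsin in both arms only the added effect of 3BNC117 can be estimated, and the reservoir analysis names no between-arm test

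*Combined protocol and SAP*

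**What the plan says.** **Objectives.** Section 3.3 gives the primary objective as "Evaluate the effects of romidepsin plus 3BNC117 or romidepsin alone on delaying or preventing viral rebound in ART-treated HIV-1-infected individuals" during ATI. The synopsis repeats it in nearly the same words. The reservoir objective is "Evaluate the effects of romidepsin plus 3BNC117 or romidepsin alone on the size of the HIV-1 reservoir in ART-treated HIV-1-infected individuals".

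**Design.** Section 4: "Participants will be randomized 1:1 in a non-blinded fashion to receive one of two regimens". Arm B is "Two treatment cycles each consisting of three romidepsin infusions", and the synopsis places the drug in both arms: "In Groups A and B, one intravenous infusion of romidepsin". Section 7.1 lists six romidepsin days per arm, two days later in arm A than in arm B. There is no ART-only, placebo or other romidepsin-free arm, and no external control is defined.

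**Hypothesis and rationale.** Section 3.2 states that the combination "will prevent or delay the return of HIV-1 viremia during an analytical treatment interruption compared with administration of romidepsin alone". The first knowledge gap at the end of section 3.1.1 is the comparison of ART plus latency-reversing agent plus antibody with ART plus latency-reversing agent, for both reservoir size and time to rebound.

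**Analysis.** In section 8.1 the primary Wilcoxon-Mann-Whitney test and the secondary log-rank test compare the two arms on time to rebound, and section 8.2 powers that comparison. For IUPM, a paired t-test or paired Wilcoxon test "will be used to determine changes in reservoir size from baseline to the pre-ATI time-point for each group". For total HIV-1 DNA, 2-LTR DNA and unspliced RNA, section 8.1 names a repeated-measures ANOVA of changes over the study and does not say that arm is a factor.

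**The concern.** An effect on delaying or preventing rebound is an effect relative to something. Time to rebound has no within-person baseline, so the effect of romidepsin alone would need participants who stop ART without having had romidepsin. None exist. The same applies to the total effect of the combination against no intervention. If both arms rebound late, or both early, the A-versus-B comparison cannot show whether romidepsin helped, harmed or did nothing.

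For rebound this stays a matter of wording, because the planned test is the right one. For the reservoir it reaches the analysis. A significant fall in IUPM within one arm could be reported as the answer to the reservoir objective although no randomised contrast had been made.

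**Working it through.** **1. Reproduce the plan's power figure.** Inputs from section 8.2: difference 13 days, SD 10 days, 12 per arm, 5% level, G*Power minimum asymptotic relative efficiency (ARE) method. Assumptions: two-sided test, minimum ARE 0.864.

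- Standardised difference: 13 / 10 = 1.3.
- Effective n per arm: 12 × 0.864 = 10.368.
- Degrees of freedom: 2 × 10.368 − 2 = 18.74.
- Noncentrality: 1.3 × √(10.368 / 2) = 2.96.
- Power from the noncentral t distribution: 0.801.

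The stated 80% is right, and it belongs wholly to arm A versus arm B. No power is given for an effect of romidepsin on rebound, and none can be derived without a romidepsin-free comparator.

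**2. Set each objective beside its analysis.**

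| Outcome | Objective (3.3) | Comparison promised in 3.1.1 or 3.2 | Analysis in 8.1 |
|---|---|---|---|
| Time to rebound | Effect of each regimen | A versus B | Between-arm test |
| IUPM | Effect of each regimen | A versus B | Within-arm paired test only |
| HIV-1 DNA | Effect of each regimen | A versus B (as reservoir size) | Change over time; arm term not stated |

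For plasma HIV-1 RNA on treatment, section 8.1 does specify a test of the proportions in the two groups. Elsewhere, then, the plan writes out a between-arm comparison when it intends one. The synopsis names the Wilcoxon-Mann-Whitney test, a two-sample test, for IUPM change, but also assigns it to each group separately. That conflicts with the paired tests in 8.1 and still gives no arm comparison.

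**3. What two within-arm p-values can say about the arms.** Suppose the arms do not truly differ and each within-arm test has the same probability *p* of reaching P < 0.05. The chance that exactly one arm is significant is 2*p*(1 − *p*). The documents give no SD for IUPM change, so *p* is an assumption, shown over a range:

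- *p* = 0.05 (no change in either arm): 2 × 0.05 × 0.95 = 9.5%.
- *p* = 0.50: 2 × 0.50 × 0.50 = 50%.
- *p* = 0.80: 2 × 0.80 × 0.20 = 32%.

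A finding of significance in one arm only is therefore no substitute for a test of the difference.

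**4. What a between-arm test could detect.** The method of step 1, solved for 80% power, gives 12.98 days with 12 per arm and 11.47 days with 15. Divided by the SD of 10, these are 1.30 and 1.15 SD. For a rank-sum test on change, the same figures apply in units of the SD of the change.

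**The case against.** The strongest reply is that the operative plan already has the right contrast. The hypothesis is comparative, there is one primary test and one power calculation, and both concern A versus B. Naming both regimens in an objective may simply be a way of listing the arms, since the same phrase appears in the safety objective, where it does no harm. All of this stands for rebound: rewording the objective changes no test, sample size or decision rule.

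A second reply is that the reservoir has a within-person baseline (week -2 against week 22 for IUPM), and section 3.1.1 describes cell-associated HIV-1 on ART as relatively stable. A before-after change is therefore interpretable to a degree. That also stands. It remains weaker evidence than the randomised contrast, and it does not supply the arm comparison that section 3.1.1 promises.

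Two stronger readings should be resisted:

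- A reader might infer that arm B's rebound times will be tested against the natural rebound of 2-3 weeks in section 3.1.1. That figure is background, and no benchmark, one-sample test or historical control is specified. It describes when most individuals rebound, so setting a confidence interval for an arm mean against it would compare unlike quantities. The futility rule in 15.9 looks at each group separately but only limits further ATI.
- A reader might infer that a delay in arm A could be direct neutralisation, because section 3.1.2.1 reports that earlier antibodies generally delayed rebound. Those antibodies were still being given during interruption. Here ATI starts 16 weeks (112 days) after the second 3BNC117 infusion. At the half-life of 17.6 days in uninfected people (3.1.2.3), that is 112 / 17.6 = 6.4 half-lives, leaving about 1% under log-linear decay. The missing 3BNC117-only arm does mean that the trial cannot show synergy, but the hypothesis does not claim it.

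**Conclusion.** The design identifies one effect: that of adding 3BNC117 to a romidepsin background. The primary and reservoir objectives should say so. The primary rebound test and its power are sound (0.801 against a stated 80%), and there the correction is wording only.

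The substantive gap is that the IUPM analysis is specified only within each group and the HIV-1 DNA analysis states no arm term. The reservoir objective would be answered without using the randomisation. This rests on section 8.1 and the synopsis as written. An arm-by-time term may have been intended in the ANOVA, but it is not stated. How far conclusions could be distorted depends on the variability of IUPM change, which the documents do not give. Under equal true change in both arms, a one-arm-only significant result would occur between 9.5% and 50% of the time over the assumed range.

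**What to change.** 1. In section 3.3 and the synopsis, restate the primary and reservoir objectives as the effect of adding 3BNC117 to romidepsin, compared with romidepsin alone.
2. In section 8.1 and the synopsis, name a between-arm comparison of the change in IUPM from week -2 to week 22. A Wilcoxon rank-sum test on change, or ANCOVA on log values adjusted for baseline, would serve. Choose one in advance, with a rule for undetectable values. For HIV-1 DNA, compare change between arms, with an arm-by-time term in the repeated-measures model. Read the contrast chiefly at week 24, because week 48 follows the interruption.
3. State that arm B rebound times and within-arm reservoir changes are descriptive and support no efficacy claim for romidepsin alone.

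The sample size, arms and visits do not change. The cost is one additional analysis with modest power (about 1.3 SD detectable with 12 per arm, 1.15 SD with 15) and the loss of a claim about romidepsin alone that the design cannot support.

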#### Secondary Objectives:

- Evaluate the safety of romidepsin plus 3BNC117 or romidepsin alone in ART-treated HIV-1 infected individuals;
- Evaluate the effects of romidepsin plus 3BNC117 or romidepsin alone on the size of the HIV-1 reservoir in ART-treated HIV-1-infected individuals;

#### Exploratory Objectives:

- Evaluate the effects of romidepsin plus 3BNC117 or romidepsin alone on HIV-1 transcriptional activity and plasma HIV-1 RNA in ART-treated HIV-1-infected individuals
- Evaluate the immunomodulatory effects of romidepsin plus 3BNC117 or romidepsin alone in ART-treated HIV-1-infected individuals.
- Evaluate the pharmacokinetics of romidepsin in HIV-1-infected individuals

### 3.4 Primary Endpoint

- Days to viral rebound during ATI or days to reinitiation of ART in participants who restart ART before viral rebound. Viral rebound is defined as HIV-1 RNA  $\geq$  200 copies/mL on 2 consecutive measurements during ATI. If viral rebound occurs, the date of the first measurement of HIV-1 RNA  $\geq$  200 copies/mL will be defined as “date of viral rebound.”

### 3.5 Secondary Endpoints

- Safety evaluation, as measured by rate and severity of adverse events (AE), serious adverse events (SAE), and serious unexpected serious adverse reactions (SUSAR).
- Size of the functional, latent HIV-1 reservoir as determined by the number of infectious units per  $10^6$  resting memory CD4+ T cells (IUPM) using a viral outgrowth assay before and after therapy. Post therapy measurements will occur after the second cycle, just before ATI. These measurements will be performed in [name] laboratory.
- Size of the proviral HIV-1 reservoir as determined by total HIV-1 DNA and episomal HIV-1 DNA (2-LTR) in circulating total CD4+ T cells at baseline, after each romidepsin cycle, prior to the ATI period (week 24), and at the end of the study (week 48).
- Plasma HIV-1 RNA, as measured by a routine clinical assay (Cobas Taqman; detection limit 20 copies/mL), a transcription mediated amplification (TMA)-based assay (detection limit 12 copies/ml) and/or a single copy assay (detection limit 1-2 copies/mL).

### 3.6 Exploratory Endpoints

- HIV-1 transcriptional activity as determined by unspliced HIV-1 RNA in circulating total CD4+ T cells.
- Phylogenetically compare viruses grown from PBMCs collected from participants while on ART to rebound viruses collected after ART interruption.
- Plasma cytokine and immune activation biomarker levels.
- Change from baseline in the capacity of NK and CD8+ T cells to mediate inhibition of viral replication ex vivo.
- Absolute cell counts and phenotypic characteristics for T and NK cells using standard cell marker panels by flow cytometry (e.g. CD3, CD4, CD8, CD45RA, CCR7 for T cells and CD16/CD56 for NK cells). Functional properties of cytotoxic T cells and NK cells will be investigated by analyzing cytokine secretion properties (e.g. IL-2, IFN- $\gamma$ , TNF- $\alpha$ ) and surface expression of CD107a/b as a surrogate marker of cytotoxic activities. CD69, CD161, NKp46, NKG2, and CD85J expression will be analysed on NK cells.
- Absolute counts, phenotypic characteristics, and functional properties of monocytes and dendritic cells using standard cell marker panels by flow cytometry.
- Romidepsin levels at the end of infusion and at 1 day after each infusion in treatment cycle 1.

### 4 Study Design

The design is a randomized interventional phase 2a trial of romidepsin with or without 3BNC117 in HIV-1-infected patients on ART, conducted as a multi-center study at the Department of Infectious Diseases, Aarhus University Hospital, Denmark, the Rockefeller University Hospital, USA, and the University Hospital of Cologne, Germany. Enrollment will be competitive; it is anticipated that each site will enroll approximately 10 participants.

[figure not shown]
Participants will be randomized 1:1 in a non-blinded fashion to receive one of two regimens:

- A) Two treatment cycles each consisting of 3BNC117 infusions (30mg/kg) + three romidepsin infusions (5mg/m^2); or
- B) Two treatment cycles each consisting of three romidepsin infusions (5mg/m^2).

ART will be discontinued 16 weeks after the start of the second treatment cycle (analytical treatment interruption, ATI) and subjects will be monitored closely for viral rebound. The study outline is shown in **Figure 1**. The targeted enrolment is 30 subjects (15 per arm).

Leukapheresis will be performed before and after the two treatment cycles to guarantee sufficient material to investigate changes in the reservoir after the interventions.

**Figure 1. Study Design**

## 5 Study Population

HIV-infected males and females, between the ages of 18-65, on ART for at least 24 months, with HIV-1 RNA plasma level of < 50 copies/ml by standard assays for at least 18 months, and with current CD4+ T cell counts > 500 cells/ $\mu$ l.

### 5.1 Inclusion Criteria

1. Adults age 18-65 years with documented HIV-1 infection
2. CD4+ T-cell count > 500 cells/mm^3 at screening
3. On ART for a minimum of 18 months and HIV-1 RNA plasma level of < 50 copies/ml by standard assays for at least 12 months (a single viral load measurement > 50 but < 500 copies/ml during this 12 month time period is allowable).

4. Individuals on protease inhibitor, NNRTI-based regimens, or regimens containing cobicistat must be willing to switch to an integrase-inhibitor-based regimen (raltegravir or dolutegravir) prior to enrollment.

## 5.2 Exclusion Criteria

1. Use of systemic corticosteroids, immunosuppressive anti-cancer, or other medications considered significant by the investigators within the last 6 months.
2. Pregnancy as determined by a positive urine or serum beta-hCG.
3. Participant unwilling to use two reliable contraception methods (i.e. condom with spermicide, diaphragm with spermicide, progestin-only containing intrauterine device (IUD) (eg, Mirena, Implanon), non-estrogen containing formulations of hormonal birth control drugs with condom) for the study duration. Romidepsin may interact with estrogen-based contraceptives and such agents may be unreliable in participants receiving romidepsin.
4. Currently breast-feeding.
5. History of resistance to 2 or more classes of antiretroviral medication.
6. Any medical, psychiatric, social, or occupational condition that, as judged by the investigators, would interfere with the evaluation of study objectives (such as severe alcohol or drug abuse, dementia, autoimmune diseases).
7. Acute or chronic hepatitis B or C infection as indicated by the presence of Hepatitis B surface antigen (HBsAg) or hepatitis C virus RNA (HCV-RNA) in blood.
8. A history of AIDS-defining illness within 3 years prior to enrollment.
9. History of B-cell lymphoma, including CNS lymphoma
10. CD4 nadir  $< 200$  cells/mm^3 within the last 5 years.
11. History of significant coronary artery disease, myocardial infarction, percutaneous coronary intervention with placement of cardiac stents, or family history of sudden death at age  $< 50$  years.
12. ECG at screening that shows QTc  $> 450$  msec when calculated using the Fridericia formula from either lead V3 or V4, pathological Q-waves (Q-wave  $> 40$  msec or depth  $> 0.4$ - $0.5$  mV), evidence of a ventricular pre-excitation syndromes, complete or incomplete LBBB or RBBB, second or third degree heart block, QRS duration  $> 120$  msec, or bradycardia defined by sinus rate  $< 50$  bps.
13. Use of QT-prolonging medication, renal or hepatic disease, structural heart disease or left ventricular dysfunction
14. Any symptomatic or asymptomatic arrhythmia excluding sinus arrhythmia or bradycardia  $\geq 50$  bps.
15. Use of Coumadin or Coumadin derivatives
16. Laboratory abnormalities in the parameters listed below:
  - a. Absolute neutrophil count  $\leq 1,000$  cells/ $\mu$ l
  - b. Hemoglobin  $< 11$  gm/dL
  - c. Platelet count  $< 125,000$  cells/ $\mu$ l
  - d. ALT  $\geq 1.25$  x ULN
  - e. AST  $\geq 1.25$  x ULN

- f. Total bilirubin > 1.0 ULN
- g. eGFR < 60 mL/min/1.73m^2
- 17. Any vaccination within 14 days prior to 3BNC117 administration;
- 18. Receipt of any therapeutic HIV vaccine in the past;
- 19. Receipt of any anti-HIV monoclonal antibody in the past, or HDAC inhibitor of any kind in the past 2 years;
- 20. Participation in another clinical study of an investigational product currently or within past 12 weeks, or expected participation during this study.

## 6 Methods and Procedures

### 6.1 Screening Procedure and Study Visits

The Time of Events Schedule summarizes the frequency and timing of various study assessments. See Appendix A. Recruitment, screening and all visits during the study period are performed either at The Rockefeller University Hospital (RUH) outpatient clinic, at the Aarhus University Hospital (AUH) outpatient clinic or at the infectious diseases outpatient clinic of the University Hospital of Cologne (UCH).

#### 6.1.1 Pre-Screening Questionnaire

Subjects eligible for enrollment might be recruited at the RUH, AUH or UCH outpatient clinics. Potential participants will first undergo pre-screening by telephone to assess medical history, preliminary HIV risk assessment, and qualification for the study. Potential volunteers will have the opportunity to discuss the study and ask questions of the study recruiter at this time. Those who are eligible and interested in participating will attend a screening visit at the RUH, the AUH or the UCH Outpatient Clinics.

#### 6.1.2 Screening Visits

##### Screening Visit (day -56 to 0):

Study personnel will answer any questions about the study. Written informed consent will be obtained prior to conducting any study procedures. To ensure informed consent, the principal investigator or designee will discuss the following processes individually with each volunteer:

1. Pregnancy avoidance counseling. Sexually active males and females, participating in sexual activity that could lead to pregnancy, should use two reliable forms of contraception for the duration of the trial.
2. Risk reduction counseling. Sexually active males and females will be asked to use condoms during the short analytical treatment interruption due to the risk of intermittent viremia.
3. One must assume that no improvement in control of HIV infection will occur given the exploratory nature of this study.
4. Subjects agree to stopping their antiretroviral medications as planned in the protocol and agree to return for scheduled follow up visits for monitoring of plasma virus levels.

If the volunteer consents to participate, site personnel will:

- Obtain a complete medical history (including concomitant medications and cardiovascular history);
- Assure that all inclusion criteria are met and there are no exclusion criteria;
- Review subject's previous HIV-1 viral load and CD4 measurements (records should be available for at least 1.5 years prior to screening);
- Perform an ECG;
- Perform a general physical examination including height, weight, vital signs (pulse, respiratory rate, blood pressure and temperature), examination of skin, respiratory, cardiovascular and abdominal systems, and an assessment of cervical and axillary lymph nodes;
- Collect blood and urine specimens for all tests as indicated in the Time of Events Schedule, including plasma HIV-1 RNA levels and CD4 counts;
- Perform a pregnancy test for all female volunteers;

